8.1 Primary Safety Outcomes

The primary safety analysis is to estimate (1) the frequency and severity of AEs, (2) the frequency of serious treatment-emergent adverse events (TEAEs), and (3) the frequency of TEAEs that result in discontinuation of the IMP.

The incidence of AEs will be summarized for the following variables:

- 1) TEAEs by severity
- 2) TEAEs potentially causally related to the IMP
- 3) TEAEs with the outcome of death
- 4) Serious TEAEs
- 5) TEAEs leading to discontinuation of the IMP
- 6) EPS-related TEAEs.

Unless specified otherwise, data summaries of the above variables will present simple descriptive statistics such as count and percentage of subjects who had at least one incidence of the AEs of interest at various summarization levels. Of note, AEs that are sex-specific (eg, ovarian cancer) will have the incidence rate evaluated for the specific sex.

Incidence and occurrence (number of events) will be provided for serious TEAEs, potentially IMP-related serious TEAEs, and nonserious TEAEs.

The incidence of TEAEs by system organ class (SOC) and preferred term (PT) will be summarized for gender, race (White, Black or African American, American Indian or Alaska Native, Asian, Native Hawaiian or Other Pacific Islander, other), region (United States [US], Europe [continent], Mexico) and age (< 15 years, \geq 15 years, based on Trial 331-10-236 entry) subgroups.

The following safety topics of interest will be provided (incidence by preferred term). The associated searching criteria base on preferred term is included in a separate document.

- EPS-related AEs (also EPS-related AEs, excluding akathisia)
- Neuroleptic malignant syndrome
- Prolactin
- QT prolongation

- Hepatic Impairment
- Effects on weight
- Effect on glucose
- Effect on lipids
- Rhabdomyolysis and CPK elevation
- Somnolence

The Medical Dictionary for Regulatory Activities (MedDRA) version 23.0 or newer will be used to code all AEs to an SOC and a PT.

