^cDose adjustments will be made weekly in 1 mg increments to a maximum of 4 mg/day.

^dVisit window of \pm 3 days will be permitted; however, every effort will be made to ensure the individual subject trial participation does not exceed 24 months.

Figure 3-2 **Trial Design Schematic - De Novo Subjects**

4 Sample Size and Power

The sample size for this trial is not based on considerations of statistical power.

Approximately 350 adolescent subjects are anticipated to be enrolled into this 24-month open-label trial with the expectation that at least 100 subjects will have had at least 12 months of exposure to the investigational medicinal product (IMP), brexpiprazole, at the conclusion of the trial.

Enrolled subjects will come from approximately 31 clinical sites across 7 countries.

It is to be noted that following the sample size reduction of the parent Trial 331-10-324 to 315 subjects (Protocol Amendment 3²), less than 350 subjects are expected in Trial 331-10-236.

5 Analysis Populations

To adequately describe the statistical analyses and reporting, three analysis populations are defined as follows.

- Enrolled Sample: consists of all consented/assented subjects who were screened for eligibility and deemed eligible (ie, deemed to have met all the inclusion and none of the exclusion criteria for the current trial).
- Safety Sample: consists of all enrolled subjects who received at least one dose of IMP (brexpiprazole). Subjects will be excluded from this population only if there was documented evidence that the subject did not take any IMP (ie, number of tablets dispensed = number of tablets returned or no IMP dispensed). If a subject was dispensed IMP, but lost to follow-up, the subject will be considered exposed to the IMP.
- Efficacy Sample: consists of all subjects in the Safety Sample who had a baseline assessment and at least one postbaseline assessment of the PANSS Total Score.

Statistical analyses (including summaries) will be performed on the Enrolled Sample for demographics, baseline characteristics, and subject disposition data; on the Safety Sample for adverse events (AEs) and other safety parameters; and on the Efficacy Sample for efficacy parameters.

To facilitate separate analysis and reporting for the 2 sequential periods (ie, the 1- to 4-week conversion period and the 24-month open-label treatment period), 2 subpopulations of the Enrolled Sample and 2 subpopulations of the Safety Sample will be derived as described below.

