10.6 Descriptive Statistics for Continuous and Categorical Variables

For continuous variables, descriptive statistics include N (ie, number of subjects with non-missing value), mean, SD, median (Med), quartile, minimum (Min), and maximum (Max). For categorical (eg, nominal or dichotomous) variables, descriptive statistics refer to frequency distribution (eg, count and percentage).

In general, ordinal variables with fewer categories (say, ≤ 4) will be handled as categorical variables, whereas ordinal variables of ≥ 5 categories (such as assessment scores on many of the scales used in this trial) will be treated as continuous.

Unless specified otherwise, the denominator used for calculating percentage will be the number of unique subjects (or say, the number of subjects "at risk") in the analysis sample (or its subgroup of interest). And whenever applicable, a row of "Missing/Unknown" will be presented along with rows of recorded outcomes for the tabulation of the categorical variables.

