10.7 Display of Statistical Output Tables and Listings

The data analysis (including summary) for the open-label treatment period will be performed on the analysis sample in aggregate as well as separately on 4 subgroups defined by prior treatment status as follows: (1) rollover subjects from Trial 331-10-234 who received the treatment with brexpiprazole 2 to 4 mg/day; (2) rollover subjects from Trial 331-10-234 who received the treatment with aripiprazole 10 to 20 mg/day; (3) rollover subjects from Trial 331-10-234 who received the treatment with placebo; and (4) de novo subjects. Thus, a statistical output table for the open-label treatment period will generally display the following 5 columns: (1) prior brexpiprazole, (2) prior aripiprazole, (3) prior placebo, (4) de novo, and (5) all.

However, in the situation where prior treatment cannot be unblinded (eg, for the interim data reporting before Trial 331-10-234 unblinding), statistical output tables will display the following 3 columns: (1) rollover, (2) de novo, and (3) all, where the “rollover” column pools together all 3 treatment groups from the parent Trial 331-10-234. It is anticipated that, at the time of data lock for the first interim data reporting, the parent trial will remain blinded.

In the situation where the number of de novo subjects participating in the cross-titration conversion period is 5 or fewer, statistical output tables will not be provided for the conversion period, but all the assessments, observations, or events collected in the conversion period will be included for data listings.

In general, data listings will not be presented separately for the open-label treatment period and the conversion period. Wherever appropriate, the listings should present a flagging variable (column) that indicates whether the listed observation is from the conversion period or not.

Wherever feasible, data listings should be sorted by trial period, prior treatment status, subject ID, date of assessment, visit, etc. And in general, the listing should present the sorting variables, baseline demographics, and all the variables of interest.

All statistical analysis and reporting will be generated using SAS® version 9.3 or higher.

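### SAP 8.1 reports adverse events as crude percentages with no time at risk; read as 24-month risks, they are too low when follow-up is incomplete and events keep arising

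*SAP*

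**What the plan says.** SAP 8.1 sets out to estimate the frequency and severity of AEs, the frequency of serious TEAEs, and the frequency of TEAEs leading to discontinuation of study drug. Unless stated otherwise, the statistic is "simple descriptive statistics such as count and percentage of subjects who had at least one incidence of the AEs of interest". The listed safety topics (EPS, weight, glucose, lipids, prolactin and others) are given as incidence by preferred term. For some classes the number of events is added: "Incidence and occurrence (number of events) will be provided for serious TEAEs, potentially IMP-related serious TEAEs, and nonserious TEAEs". No time denominator is attached to those counts.

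SAP 10.6 fixes the default denominator: "the denominator used for calculating percentage will be the number of unique subjects" in the analysis sample or subgroup. It glosses this as subjects at risk, but that is still a head count. Under SAP 5, a subject who was dispensed drug and then lost to follow-up counts as exposed.

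SAP 8.1.1 counts AEs up to 30 days after the last dose. It plans two Kaplan-Meier curves: discontinuation due to AE or death, with other exits censored, and discontinuation for any reason. SAP 8.4.1 tabulates exposure separately. Under SAP 10.7, "a statistical output table for the open-label treatment period will generally display the following 5 columns", four defined by prior treatment status and one total.

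The planning figures are in SAP 4. Enrolment is put at about 350, "with the expectation that at least 100 subjects will have had at least 12 months of exposure". After the parent trial was reduced to 315 subjects, "less than 350 subjects are expected in Trial 331-10-236".

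**The concern.** The trial asks about safety over a 24-month treatment period. A crude percentage counts a subject who left in Week 2 without an event in the same way as one followed event-free for two years. It therefore mixes the rate at which events occur with how long subjects stayed. For events that go on arising, a reader who takes the percentage as a long-term risk will take it as too low.

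Unequal follow-up does not depend on dropout alone. SAP 9.2 plans one data report when about 100 subjects have six months of exposure and another about six months after the last subject enters. SAP 10.5 anticipates many ongoing subjects at the interim lock, and the protocol synopsis allots 40 months to recruitment. Observed time at those cuts will vary with date of entry, so the same percentage can mean different things in different reports.

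**Working it through.** **Inputs from the documents.** About 350 enrolled and at least 100 with 12 months of exposure (SAP 4); a 24-month treatment period; AE window to 30 days after last dose (SAP 8.1.1). The documents state no dropout rate, no AE rate and no retention by column, so there is no planned figure to reproduce.

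**Assumptions.** Constant AE rate r per year, constant dropout rate d per year, and dropout independent of AEs. The values of r are illustrative.

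**Step 1: the retention floor.** 100/350 = 28.6% at 12 months (100/315 = 31.7%). Then d = −ln(100/350) = 1.253 per year. The share still on drug at 24 months is (100/350)² = 8.2%, about 29 of 350. Mean exposure is (1 − 0.082)/1.253 = 0.73 years, or 8.8 months.

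**Step 2: crude percentage against 24-month risk.**
- Expected crude proportion = r/(r+d) × [1 − exp(−2(r+d))]
- 24-month risk = 1 − exp(−2r)

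For r = 0.10 at the floor: 0.10/1.353 × [1 − exp(−2.706)] = 0.0739 × 0.933 = 6.9%. The risk is 1 − exp(−0.20) = 18.1%.

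| 12-month retention | r = 0.10: crude (risk 18.1%) | r = 0.30: crude (risk 45.1%) |
|---|---|---|
| 28.6% (100/350) | 6.9% | 18.5% |
| 31.7% (100/315) | 7.4% | 19.6% |
| 50% | 10.0% | 26.1% |
| 70% | 13.1% | 33.4% |

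**Step 3: sensitivity at the floor.**
- Counting events for 30 days after each exit raises 6.9% to 7.7% and 18.5% to 20.4%.
- Shape of dropout, for a true 24-month risk of 20%: constant dropout gives 7.6%; constant dropout to month 12 and none afterwards gives 8.8%; all dropouts leaving exactly at month 12 gives 13.3%.
- Timing of events, for a true risk of 20% confined to the first 1, 2, 3 or 6 months: the crude figure is 19.0%, 18.1%, 17.3% or 15.0%.

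**Step 4: comparing columns.** Take a true 24-month risk of 20% in both columns. Equal retention of 28.6% gives 7.6% against 7.6%. Retention of 28.6% against 50% gives 7.6% against 11.1%. At 25% against 32% it is 7.1% against 8.2%.

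**Step 5: interim reports.** With no dropout at all, a subject observed for six months at r = 0.10 has a probability of 1 − exp(−0.05) = 4.9% of showing the event, against 18.1% for one observed for 24 months.

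**Step 6: what a person-time denominator does.** For r = 0.10 at the floor, mean time to first event or exit is 0.933/1.353 = 0.690 years. The first-event rate is 0.0690/0.690 = 0.10, that is 10 per 100 person-years. The underlying rate is recovered whatever the retention, as long as the assumptions hold.

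**The case against.** The strongest reply is that the percentage is a well-defined description: the share of treated subjects who had an event while observed. The SAP speaks of frequency and incidence, never of a 24-month risk, and the protocol synopsis rules out inferential analysis. That stands. The point concerns what the table can be used for, not an error in the statistic.

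Four stronger readings are tempting, and the documents do not support them.

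- **That the plan expects about 71% of subjects to leave before 12 months.** It says "at least 100 subjects will have had at least 12 months of exposure to the investigational medicinal product". That is a minimum, and no dropout rate is given. The 28.6% row is the worst case the plan tolerates.
- **That the whole primary analysis is crude.** Discontinuation due to AEs is one of the three primary components, and it has a Kaplan-Meier curve that censors other exits. Event counts are also planned for some classes.
- **That late weight and metabolic effects would be lost.** SAP 8.2.1 and 8.2.3 summarise laboratory values, weight and z-scores by visit on observed cases, and tabulate weight changes of 7% or more by visit. Late change is visible among those still assessed. Only the AE-term incidences and the overall-period incidences ignore time.
- **That the columns cannot be compared.** With equal exposure they shrink alike. Nothing in the documents indicates unequal retention, the fifth column is a total, and exposure is generally shown in the same columns, so an imbalance would be visible.

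Visible exposure does not supply the missing rate, however. A reader cannot rebuild time to first event from a separate exposure table.

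**Conclusion.** The point holds in limited form. TEAEs, serious TEAEs and the topics of interest have no time-at-risk denominator in a trial about long-term safety, while discontinuation does get a time-to-event analysis. If the percentages are read as 24-month risks, the shortfall for continuing events is more than half at the retention floor (6.9% against 18.1%), about a quarter at 70% retention (13.1% against 18.1%), and slight for events confined to the first weeks. These sizes rest on constant hazards and independent dropout, and the AE rates are illustrative; other dropout shapes change the size but not the direction. Distortion between columns, or between interim and final reports, is conditional on exposure differing. Differing exposure is likely at the interim cuts because of staggered entry; between columns it is only possible. This is a cheap improvement to reporting and does not invalidate the planned tables.

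**What to change.** In SAP 8.1, keep the crude percentages and add two things.

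1. In every column, give the first-event rate per 100 person-years with a 95% confidence interval for any TEAE, serious TEAEs, TEAEs leading to discontinuation, and the listed safety topics. Person-time runs to the earliest of first event, last contact, or 30 days after last dose, matching the SAP 8.1.1 window. Ending at last contact also deals with subjects lost after dispensing and with those ongoing at an interim lock.
2. For the main topics, give cumulative incidence at 6, 12 and 24 months for all subjects combined, with numbers at risk.

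The cost is SAP wording and extra table columns, using event, dose and contact dates already collected. No visit or clinical procedure changes, and descriptive intervals are compatible with a plan that tests nothing. Three limits should be stated beside the results. The rates summarise a roughly constant hazard; cumulative incidence at several times helps show where that fails. Both estimates assume non-informative censoring. The 24-month estimates will be imprecise if few subjects remain (about 8% at the floor under constant dropout), which is why cumulative incidence is proposed for the total and not by column.

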8.1.1 Data Collected in the Open-label Treatment and the Follow-up Period

A TEAE in the open-label treatment period is defined as an AE that starts after the first dose of IMP upon entering the open-label treatment period, or an AE that is present at baseline of the open-label period and increases in intensity or becomes serious or IMP-related or results in death, discontinuation, interruption, or reduction of the IMP.

Any AEs occurring up to 30 days after the last dose of IMP in the open-label treatment period will be included in the AE summary tables. AEs having occurred 30 days after the last dose of IMP, if collected, will be reported in listings only.

In addition, a Kaplan-Meier curve will be plotted for the time (in months) from Day 1 of the open-label treatment to the discontinuation of IMP due to AEs or death. The subject will be censored if he or she discontinues the treatment due to any other causes (other than AEs or death) or loss to follow-up at any time points before the end of the open-label treatment period. In addition, subjects will be censored at the end (ie, the Month 24 visit) of the open-label treatment period if they stay in treatment beyond the end time point. A Kaplan-Meier curve will be plotted for the time (in months) from Day 1 of the open-label treatment to the discontinuation of IMP due to any reason.

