| Trial Duration: | 
The duration of this trial from first subject enrolled to last subject completed is estimated to be approximately 66 months, of which 40 months are allotted for recruitment of subjects. Individual participation for rollover subjects who complete the trial without early withdrawal will be approximately 25 months, consisting of a 24-month open-label treatment period, and a 21 (<math>\pm 2</math>)-day follow-up, if applicable. Individual participation for de novo subjects who complete the trial without early withdrawal will be approximately 27 months, consisting of a screening period of up to 28 days, a conversion period of 1 to 4 weeks, a 24-month open-label treatment period, and a 21 (<math>\pm 2</math>)-day follow-up, if applicable.
 |

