### **3.5.2      Secondary Endpoints**

#### **3.5.2.1      Secondary Safety Endpoints**

The secondary safety endpoints are as follows:

- Mean change from baseline and incidence of clinically significant abnormalities in clinical laboratory tests and urinalysis results (including fasting blood lipids, glucose and insulin, serum prolactin, glycosylated hemoglobin [HbA1c] and creatine phosphokinase [CPK]), vital signs (supine and standing positions), weight, height, body mass index (BMI), waist circumference, and ECG parameters
- Mean change from baseline on the Abnormal Involuntary Movement Scale (AIMS), Simpson-Angus Scale (SAS), and Barnes Akathisia Rating Scale (BARS)
- Analysis of potential suicide events recorded on the Columbia-Suicide Severity Rating Scale (C SSRS)

- Comprehensive psychotropic side effects as assessed by Udvalg for Kliniske Undersøgelser (UKU) side effect rating scale
- The frequency of symptom items for the clinician-administered New York Assessment for Adverse Cognitive Effects of Neuropsychiatric Treatment: (NY-AACENT)
- Baseline and postbaseline Tanner Staging Scale data
- Time to discontinuation due to AE

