## **7 Statistical Analysis**

### **7.1 Sample Size**

The sample size is not based on statistical power considerations. Approximately 350 subjects are anticipated to be enrolled with the expectation that at least 100 adolescent subjects with schizophrenia will complete a minimum of 1 year of exposure to open-label brexpiprazole.

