9.2 Interim Analysis

There will be an interim data reporting when approximately 100 subjects have had at least 6 months of exposure to the IMP in the 24-month open-label treatment period. An additional interim analysis will be performed approximately 6 months after the last subjects enters the trial.

All collected data including all safety and efficacy data will be reported for the interim data reporting. Database lock will be executed for the interim data reporting.

The final analysis will be performed upon completion of the trial. Database lock will be executed for the final analysis.

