10.5 Data Imputation for the Last Assessment Visit

A landmark time point for the trial is the end-of-trial visit (the Month 24 visit) in the open-label treatment period of the trial. For some reason, a subject may be discontinued early from treatment before the end-of-trial visit. Such a subject will be invited to an ET visit where the assessments originally scheduled for the Month 24 visit will be collected.

It is anticipated that there will be many ongoing subjects at the time of the interim analysis database lock. For purposes of the interim data reporting, the LOCF rule will be applied to all subjects (including all ongoing subjects) in deriving the last visit's value for the subjects. If this trial is completed to the extent that the last enrolled subject has had an

opportunity to complete 24 months' open-label treatment, then the value at the 24-month visit or at the ET visit will be taken as the value for the last visit.

In deriving the last visit data, the LOCF rule will be applied to the following parameters: PANSS (including Total Score, Positive subscale score, Negative subscale score), CGI, SAS, AIMS, BARS, body weight, waist circumference, height, BMI, vital signs, ECG, clinical laboratory tests, CGAS, NY-AACENT, UKU Side Effects Rating Scale, Tanner Staging, and pregnancy tests. The LOCF rule will also be applicable to the individual PANSS items in deriving the last visit data. Note that only the postbaseline data can be carried forward in deriving the last visit data.

In general, the by-visit analysis (eg, summary) of a variable will also include the analysis for the derived last visit.

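### The only time-to-event analysis of AE discontinuation is a Kaplan-Meier curve that censors all other stops; read as a risk, it overstates how many subjects actually stop because of an AE

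*SAP*

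**What the plan says.** Protocol 3.5.2.1 names "Time to discontinuation due to AE" as a secondary safety endpoint, and Protocol 7.5.1 plans only a KM curve for it. SAP 8.1.1 widens the event to IMP discontinuation due to AE or death, measured in months from open-label Day 1. A subject "will be censored if he or she discontinues the treatment due to any other causes (other than AEs or death) or loss to follow-up"; subjects still on treatment at Month 24 are censored there. Neither document mentions competing events or cumulative incidence.

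Three other planned outputs are related:

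- SAP 8.1 gives "the frequency of TEAEs that result in discontinuation of the IMP" as a primary safety outcome, in counts and percentages of subjects.
- SAP 6.1 tabulates reasons for discontinuation.
- SAP 8.1.1 adds a KM curve for discontinuation for any reason.

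All safety data are also reported at two interim database locks (SAP 9.2). The first comes when about 100 subjects have at least 6 months of exposure. Of the second the SAP says: "An additional interim analysis will be performed approximately 6 months after the last subjects enters the trial". SAP 10.5 adds: "It is anticipated that there will be many ongoing subjects at the time of the interim analysis database lock".

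**The concern.** Censoring is right for a subject whose event could still happen unobserved. A subject who has stopped IMP because of withdrawn consent, pregnancy or a non-medical reason (all listed in Protocol 3.8.3.3) cannot later stop it because of an AE. Treating that stop as censoring makes 1-KM answer a different question: how many would stop for an AE if nobody ever stopped for anything else.

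The trial exists to describe long-term tolerability, and this curve is the only analysis given for a named tolerability endpoint. Anyone reading 6-, 12- or 24-month risks off the plot would get values that are too high. The other outputs do not fill the gap. The crude percentage and the reasons table have no time axis, and the any-reason curve describes a different event. At the interim reports the crude percentage also mixes subjects with different lengths of follow-up.

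**Working it through.** The documents give no dropout rate, AE-discontinuation rate or expected event count for this trial, so there is no figure of the plan's own to reproduce. What follows is an illustration on stated assumptions.

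**Inputs from the documents**
- Horizon: 24 months (SAP 8.1.1).
- Retention: only a floor. Protocol 7.1 says: "Approximately 350 subjects are anticipated to be enrolled with the expectation that at least 100 adolescent subjects with schizophrenia will complete" at least 1 year of exposure. 100/350 = 28.6%.
- SAP 4 says "less than 350 subjects are expected in Trial 331-10-236" after the parent trial was cut to 315. If enrolment is no larger than that, the floor is 100/315 = 31.7%.
- Recruitment: the Trial Duration entry of the Protocol Synopsis gives the trial's total length, "of which 40 months are allotted for recruitment of subjects".

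**Assumed**
- 12-month retention R of 28.6%, 31.7%, 50% or 70%.
- AE share s of the discontinuation hazard of 10%, 20% or 30%.
- Constant hazards, unless stated otherwise.

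**Formulas**, per year
- Total hazard H = -ln(R); AE hazard = sH.
- 24-month 1-KM = 1 - exp(-2sH).
- 24-month cumulative incidence (CIF, the actual risk) = s × [1 - exp(-2H)].

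Example, R = 50% and s = 0.10: H = 0.6931. 1-KM = 1 - exp(-0.1386) = 12.9%. CIF = 0.10 × (1 - 0.25) = 7.5%. Ratio 1.73.

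| 12-month retention | H | s = 10%: 1-KM vs CIF | s = 20% | s = 30% | Ratios |
|---|---|---|---|---|---|
| 100/350 (floor) | 1.2528 | 22.2 vs 9.2% | 39.4 vs 18.4% | 52.8 vs 27.6% | 2.41 / 2.15 / 1.92 |
| 100/315 | 1.1474 | 20.5 vs 9.0% | 36.8 vs 18.0% | 49.8 vs 27.0% | 2.28 / 2.05 / 1.84 |
| 50% | 0.6931 | 12.9 vs 7.5% | 24.2 vs 15.0% | 34.0 vs 22.5% | 1.73 / 1.61 / 1.51 |
| 70% | 0.3567 | 6.9 vs 5.1% | 13.3 vs 10.2% | 19.3 vs 15.3% | 1.35 / 1.30 / 1.26 |

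Constant hazards carry year-1 dropout into year 2, so Month 24 retention is R squared: 8.2% at the 100/350 floor, 25% in the 50% row and 49% in the 70% row.

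**Other shapes** (ratios for s = 10/20/30%)
- Floor, no dropout of any kind in year 2: 11.8 vs 7.1%, 22.2 vs 14.3%, 31.3 vs 21.4%; ratios 1.65 / 1.55 / 1.46.
- AE stops confined to the first 6 months, with s the AE share of the 12-month cumulative hazard: floor 1.30 / 1.26 / 1.22; 50% retention 1.16 / 1.14 / 1.12.
- AE stops confined to the first 3 months: floor 1.14 / 1.12 / 1.11; 50% retention 1.08 / 1.07 / 1.06.

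**Simulation check.** With 350 subjects, 1,000 runs and a true 24-month risk of 7%, mean 1-KM / Aalen-Johansen / crude percentages were 17.5 / 7.0 / 7.0 at the floor, 12.2 / 7.1 / 7.1 at 50% retention and 9.2 / 6.9 / 6.9 at 70%. With complete follow-up, crude and Aalen-Johansen agree; 1-KM does not.

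**Second interim.** With entry assumed uniform over 40 months, possible follow-up is min(24, 6 + U) months, U uniform on 0 to 40. The fraction with under 24 months is (24 - 6)/40 = 45%. At s = 10%, crude vs 24-month CIF is 8.5 vs 9.2% (floor), 6.6 vs 7.5% (50%) and 4.4 vs 5.1% (70%). At 50% retention the corresponding 1-KM is 12.9%.

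**Loss to follow-up** (floor, s = 10%, losses assumed to be 10% or 20% of the discontinuation hazard). CIF is 9.2% if losses are a competing event, 9.9% or 10.8% if they are censored, and 18.4% or 27.6% if every loss were really an AE stop.

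**Comparing columns.** Take two groups with the same AE hazard, 0.1253 per year, and non-AE hazards of 1.1275 and 0.30. 1-KM is 22.2% in both; CIF is 9.2% and 16.9%. KM is therefore the better tool for comparing AE hazards between the prior-treatment columns.

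**The case against.** The strongest reply is that the plan contains no wrong number. It asks for a curve, not a 1-KM percentage, and the error arises only when a reader converts one to the other. Censoring other causes is a legitimate way to describe AE discontinuation in the hypothetical absence of other stops, if those stops are independent of AE stops. The crude percentage is a primary outcome, unaffected by this, and at the final analysis it is close to the 24-month risk. At the second interim, with a 10% AE share, it falls short of the 24-month CIF by less than 1 point, and over all the shares and retentions above by at most about 2.6 points. The trial is descriptive, and nothing in the documents shows a decision resting on this curve.

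The large ratios also need caution. 100/350 is a minimum, not a forecast, and the protocol counts everyone who signs consent as enrolled, so retention among treated subjects may be higher. AE shares of 20 to 30% imply actual risks of 10 to 28%. The only AE-discontinuation figure in the documents is 7.0% (312/4488, Protocol 1.3), pooled over trials of differing length. The uniform-entry assumption ignores the enrolment pause mentioned in SAP 7.1.1.

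All of this stands as a limit on weight. It does not supply the missing output: no planned analysis shows the actual AE-discontinuation risk at 6 or 12 months, or at any fixed time while many subjects are still on treatment.

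**Conclusion.** The concern holds, with modest weight. The direction is certain: 1-KM is never below the cumulative incidence, and exceeds it whenever a non-AE stop precedes an AE stop. The size is not fixed by the documents. Across the scenarios above it runs from about 1.06-fold (50% retention, AE stops only in the first 3 months) to 2.4-fold (constant hazards at the planning floor). The middle case of constant hazards and 50% retention gives 1.5- to 1.7-fold. Retention, AE share and AE timing are all assumed. The crude primary percentage is not biased by the censoring rule, and the KM curve remains valid for comparing AE hazards. The change should be made, but no conclusion of the trial depends on it.

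**What to change.** In SAP 8.1.1:

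1. Add an Aalen-Johansen cumulative incidence curve for IMP discontinuation due to AE or death. Treat discontinuation for other known reasons as the competing event, and censor administratively at Month 24 or data cut-off.
2. Report 6-, 12- and 24-month values at the final analysis, and at the interim reports where follow-up allows.
3. State how loss to follow-up is handled: as a competing event in one analysis, and censored in a sensitivity analysis.
4. Keep the KM curve the protocol requires, labelled as assuming no other discontinuation, and use it to compare AE hazards between prior-treatment columns. Keep the any-reason KM curve as planned.

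The cost is two or three sentences, a few lines of code, one extra figure and one sensitivity run. Reasons for discontinuation are already recorded (Protocol 3.8.3.2), so no new data are needed.
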